### 4. ELIGIBILITY ASSESSMENT

#### 4.1 Inclusion criteria

- 4.1.1 Diagnosis of MDS, with WHO classification of refractory anemia, refractory cytopenia with unilineage dysplasia (RCUD), RARS, RCMD-RS, or RCMD
- 4.1.2 IPSS risk scores of low, intermediate-1, or intermediate-2.
- 4.1.3 Platelet count  $\leq 30,000/\mu\text{L}$  or platelet-transfusion-dependence (requiring at least 4 platelet transfusions in the 8 weeks prior to study entry); OR hemoglobin less than 9.0 gr/dL or red cell

- transfusion-dependence (requiring at least 4 units of PRBCs in the eight weeks prior to study entry) OR ANC $\leq$ 500
- 4.1.4 Age  $\geq$  18 years old
  - 4.1.5 Treatment naïve or off all other treatments for MDS (except stable dosing of filgrastim (G-CSF), erythropoietin, and transfusion support) for at least four weeks. G-CSF can be used before, during and after the protocol treatment for subjects with documented neutropenia (<500/UL) as long as they meet the criteria for other cytopenias as stated above. G-CSF must be held for 3 weeks prior to enrollment bone marrow biopsy and prior to each study assessment bone marrow biopsy, unless clinically indicated to avoid infections per PI discretion.
  - 4.1.6 Adequate liver function, as evidenced by total serum bilirubin  $\leq$  1.5 times the upper limit of normal (patients with Gilbert's disease are eligible, provided intermittent indirect hyperbilirubinemia, AST or ALT  $\leq$  5 times the upper limit of normal).
  - 4.1.7 A serum creatinine concentration  $\leq$  2 x ULN

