Criteria for response to the primary endpoint: A treatment response will be any increase in a cytopenia in the lineage that fulfilled eligibility criteria for enrollment, which is defined as follows. Platelet response is defined as platelet count increases to 20,000/ $\mu$ L above baseline at 16 or 20 weeks, or stable platelet counts with transfusion independence for a minimum of 8 weeks in subjects who were previously transfusion dependent. In the event that a subject is transfused platelets for a count >10,000/ $\mu$ L without a medical indication during the study period, the subject may continue on study drug and the response assessment may be extended for an additional 4 weeks, to week 20, at the discretion of the principal investigator. Subject being evaluated for platelet, erythroid, or neutrophil responses, may have the response assessment extended an additional 4 weeks, to week 20, at the discretion of the principal investigator. Erythroid response for subjects with a pretreatment hemoglobin of less than 9 g/dL will be defined as an increase in hemoglobin by  $\geq 1.5$ g/dL without packed red blood cell (PRBC) transfusion support, or a reduction in the units of PRBC transfusions by at least 50% during the eight consecutive weeks prior to response assessment -compared with the pretreatment transfusion number in the previous 8 weeks. Neutrophil response will be defined in those with a pretreatment absolute neutrophil count (ANC) of  $<0.5 \times 10^9/L$  as at least a 100% increase or an absolute increase  $> 0.5 \times 10^9/L$ . Subjects with a platelet, erythroid, and/or neutrophil response at 16 to 20 weeks may continue study medication (extended access) until they meet an off study criteria. Subjects with erythroid, or neutrophil response at 16 weeks may continue study medication for an additional 4 weeks (to ensure eligibility) prior to being consented for entry into the extended access part of the trial. Patients may remain on the extended access until they meet an off study criteria.

*Transfusion Units:* Single donor apheresis platelets have become the primary source of platelets in the US. Therefore, one transfused, single donor platelet apheresis product is considered 1 unit for protocol purposes. In the rare case that a patient received pooled platelet products, each completed platelet transfusion (1 bag) independent of donor units pooled, will be counted as 1 unit transfused.

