## 8.2 Endpoints

The **primary endpoint** will be the portion of drug responders as defined by changes in the platelet count and/or platelet transfusion requirements or the proportion of subjects who meet erythroid response or neutrophil response criteria Platelet response is defined as platelet count increases to 20,000/ $\mu$ L above baseline at 16 to 20 weeks, or stable platelet counts with transfusion independence for a minimum of 8 weeks. Erythroid response for subjects with a pretreatment hemoglobin of less than 9 g/dL will be defined as an increase in hemoglobin by  $\geq 1.5$ g/dL without packed red blood cell (PRBC) transfusion support, or a reduction in the units of PRBC transfusions by at least 50% during the eight consecutive weeks prior to response assessment - compared with the pretreatment transfusion number in the previous 8 weeks. Neutrophil response will be defined in those with a pretreatment absolute neutrophil count (ANC) of  $<0.5 \times 10^9/L$  as at least a 100% increase or an absolute increase  $> 0.5 \times 10^9/L$ . Subjects with a platelet, erythroid, and/or neutrophil response at 16 to 20 weeks may continue study medication (extended access) until they meet an off study criteria. Subjects with erythroid, or neutrophil response at 16 weeks may continue study medication for an additional 4 weeks (to ensure eligibility) prior to being consented for entry into the extended access part of the trial. Patients may remain on the extended access until they meet an off study criteria.

The toxicity profile will be measured using the CTCAE Version 4.0 criteria.

**Secondary endpoints** will include incidence of grade 2 or higher bleeding events as measured by

CTCAE v. 4.0; changes in serum thrombopoietin level, measured at 16 to 20 weeks; progression to higher risk MDS as measured by IWG criteria; and discontinuation of drug in robust responders enrolled in extended access.

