### 8.3 Sample Size

Because the efficacy of eltrombopag in this subject population is unknown, we would like to reject the treatment as quickly as possible with a small number of subjects if the treatment is not effective. In our past experience with this patient population, a novel treatment with a response rate 30% or more would generally warrant further investigation, while the treatment would be rendered non-effective if it has a response rate of 10% or less. We will use Simon's Two-Stage Minimax Design with a response probability of 10% or less to terminate the treatment and the hypothesized actual response probability of 30% or more. The sample size is determined by testing the null hypothesis  $H_0: p \leq 10\%$  versus the alternative  $H_1: p \geq 30\%$  at a significance level of 0.05 and a power of 0.8. At the first stage, 15 subjects will be accrued. Further accrual will be halted until the all 15 subject reach the 16 to 20 weeks response time point. The null hypothesis will not be rejected if no more than 1 subject responds to the treatment within 16 to 20 weeks. If 2 or more subjects respond to the treatment within 16 to 20 weeks at the first stage, then an additional 10 subjects will be accrued, bringing the total number of subjects to  $n = 25$ . The null hypothesis of  $p \leq 10\%$  will be accepted if the total number of responders within 4 months is 5 or less.

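### Neutrophil response reduces to a doubling of ANC, because joining the limbs with 'or' makes the absolute-increase limb redundant, so trivial rises from very low counts become primary-endpoint successes

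*Combined protocol and SAP*

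**What the plan says.** Section 8.1 describes a treatment response as "any increase in a cytopenia in the lineage that fulfilled eligibility criteria for enrollment". For neutrophils the rule covers subjects with pretreatment ANC below 0.5 x 10^9/L and defines response "as at least a 100% increase or an absolute increase" above 0.5 x 10^9/L. The same rule stands in Section 8.2 and twice in the Precis (the treatment-response paragraph and the primary-endpoint paragraph).

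Section 8.2 puts this into the primary endpoint: a subject may count through platelets, "or the proportion of subjects who meet erythroid response or neutrophil response criteria". Section 8.4 records that Amendment L moved erythroid and neutrophil response from secondary to primary.

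The neutrophil entry criterion in Section 4.1 is an alternative to the platelet and red-cell criteria: "in the eight weeks prior to study entry) OR ANC $\leq$ 500". Section 4.1 also states that "G-CSF can be used before, during and after the protocol treatment for subjects with documented neutropenia", provided another cytopenia criterion is met.

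Section 8.3 sets the test. A drug that reaches 30% is judged worth pursuing. At the lower end, "the treatment would be rendered non-effective if it has a response rate of 10% or less". The Simon minimax design is specified "at a significance level of 0.05 and a power of 0.8": 15 subjects, stop at 1 or fewer responders; otherwise 25 subjects, with H0 rejected at 6 or more.

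**The concern.** A two-limb rule normally has two limbs because each does some work. Here the baseline ceiling and the absolute threshold are the same number, 0.5 x 10^9/L. Joined by *or*, the absolute limb is swallowed by the percentage limb, and the rule has no floor for subjects who start very low.

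The protocol's other count criteria do have floors: 20,000/µL for platelets and 1.5 g/dL for hemoglobin. A neutrophil rise of 0.05 or 0.10 x 10^9/L has none to clear. Such a subject is a success in a design that needs only 6 in 25, yet can still be as neutropenic as the entry criterion requires, and below the 500/µL level that Section 5.5 treats as a loss of adequate counts. A rule that ordinary count variation can satisfy also puts in doubt whether 10% still describes an ineffective treatment for this composite endpoint.

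**Working it through.** **1. The design as stated.** Inputs from Section 8.3: n1 = 15, r1 = 1, n = 25, r = 5. The probability of rejecting H0 is the sum over x = 2 to 15 of P(X1 = x) × P(X2 ≥ 6 − x), with X1 ~ Bin(15, p) and X2 ~ Bin(10, p).
- p = 0.10: 0.0328
- p = 0.30: 0.8017

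The stated design is reproduced and meets its alpha and power. Rejection reaches 0.05 at p ≈ 0.1105, so about one percentage point of extra response uses up the margin.

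**2. The redundancy.** Let b be the baseline and d the increase, in 10^9/L. If 0 < b < 0.5 and d > 0.5, then d > b, so d/b > 100%. The absolute limb lies wholly inside the percentage limb. Enumeration over baselines 1 to 499/µL and final counts 0 to 3000/µL agrees:

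| Limb met | Baseline/final pairs |
|---|---|
| absolute only | 0 |
| percentage only | 125,249 |
| both | 1,122,750 |

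The one exception is b = 0, where a percentage change is undefined and only the absolute limb can be used.

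**3. What each rule demands** (cells/µL):

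| Baseline | As written: final at least | Absolute limb binding: final above |
|---|---|---|
| 50 | 100 | 550 |
| 100 | 200 | 600 |
| 200 | 400 | 700 |
| 400 | 800 | 900 |

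As written, any subject starting at 250/µL or lower can respond with a final ANC of 500/µL or less, because 2 × 250 = 500. With the absolute limb binding, the final count always exceeds 500/µL.

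**4. Safeguards looked for.**
- The eligible-lineage limit in Section 8.1 does not help: every subject with ANC below 0.5 x 10^9/L meets the ANC entry criterion.
- Section 6.1 requires a blood count within 72 hours of the first dose, but nothing says pretreatment ANC is averaged or confirmed.
- Section 8.1 allows a second assessment at week 20 at the investigator's discretion.
- The response rule has no G-CSF condition. The G-CSF hold in Sections 4.1 and 5.6 is tied to marrow examinations, and Section 4.1 allows it to be waived to avoid infection.

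**5. Chance doubling (assumption).** The documents give no ANC variability. Assume a within-subject SD of log ANC, s, of 0.3 to 0.5 and no drug effect. The log ratio of two counts has SD s√2, so q = P(Z ≥ ln 2 / (s√2)).
- s = 0.3: 0.693/0.424 = 1.634, q = 5.1%
- s = 0.5: 0.693/0.707 = 0.980, q = 16.3%

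With the absolute limb binding, q = P(Z ≥ ln((b + 0.5)/b) / (s√2)): 0.2% to 3.8% at b = 0.2, and 1.0% to 8.3% at b = 0.3.

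**6. Effect on type I error (assumption).** Let f be the share of subjects with ANC below 0.5 x 10^9/L, also not given. If chance doublings add independently to a 10% rate, p = 1 − 0.9(1 − fq):

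| f | p | P(reject H0) |
|---|---|---|
| 10% | 10.5% to 11.5% | 4.0% to 5.8% |
| 20% | 10.9% to 12.9% | 4.8% to 9.3% |
| 30% | 11.4% to 14.4% | 5.6% to 13.9% |

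The error passes 5% once fq exceeds about 1.2%.

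**The case against.** **The rule may have been meant this way.** The redundancy does not prove that *and* was intended. Under *and* the 100% limb becomes the idle one, since for baselines below 0.5 a rise above 0.5 always exceeds 100%. The criteria are attributed to a cited reference that is not available here. This stands: the documents do not show what the authors meant. They do show that the rule as written lets a subject succeed while still meeting the neutropenia entry criterion, and that is enough to call for a correction.

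**The type I error is not shown to be breached.** A reader might infer that the error exceeds 0.05. The documents do not support that. The additive model presumes a 10% response rate already present and puts chance doublings on top, and Section 8.3 does not say that its 10% excludes chance responses. If the drug did nothing and ANC noise were the only source of response, the overall rate fq would be 1.0% to 3.3% with 20% neutropenic and 2.6% to 8.2% with 50%, all below 10%. Chance responses in the other lineages would add to this but are not quantified. Even on the additive model, low f with low q stays within 0.05. Section 2.1 calls neutropenia less common, and Section 5.2 expects enrolment for anemia and/or thrombocytopenia, so f may be small. This stands, and it limits the claim about size.

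**The definition does more than count successes.** It also decides who may enter extended access and who stops for non-response (Precis, Sections 3, 5.5, 8.1 and 8.6.2). This stands too, so the change is not purely editorial.

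**Conclusion.** The point holds as a defect of the counting rule. For every baseline above 0 and below 0.5 x 10^9/L the absolute limb adds no responder, the rule is a doubling of ANC, and rises such as 0.05 to 0.10 or 0.10 to 0.20 are primary-endpoint successes with nothing elsewhere to limit them. This follows from the documents alone and needs no assumption.

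The consequence for the test is conditional. The Simon calculation itself is sound. On the additive model, type I error runs from 4.0% (10% neutropenic, log-ANC SD 0.3) to 13.9% (30% neutropenic, SD 0.5), against 3.3% at exactly 10%. The neutropenic share, the ANC variability and the independence of chance doublings from other responses are all assumptions. A breach of 0.05 is possible but not demonstrated. The rule should be corrected because it is easy to fix and feeds directly into the primary count.

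**What to change.** For the primary-endpoint count in the Simon analysis, make the absolute limb bind: require an increase in ANC above 0.5 x 10^9/L at the week 16 or 20 assessment. For baselines below 0.5 this is what *and* amounts to; the 100% limb is then met automatically and can be dropped. It also works at a baseline of 0. Edit all four places: both Precis paragraphs, Section 8.1 and Section 8.2. Report subjects who double their ANC without meeting the absolute limb as responders in a sensitivity analysis, so that the effect of the choice is visible.

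The same definition governs entry to extended access and stopping for non-response. The sponsor must therefore reconcile the Precis and Sections 3, 5.5, 8.1 and 8.6.2 with the corrected endpoint definition; no treatment rule is proposed here.

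Cost: four short edits and that reconciliation. The 1/15, 5/25 design is unchanged. A few marginal neutrophil responders would no longer count, so the observed response rate may be slightly lower.

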## 8.2 Endpoints

The **primary endpoint** will be the portion of drug responders as defined by changes in the platelet count and/or platelet transfusion requirements or the proportion of subjects who meet erythroid response or neutrophil response criteria Platelet response is defined as platelet count increases to 20,000/ $\mu$ L above baseline at 16 to 20 weeks, or stable platelet counts with transfusion independence for a minimum of 8 weeks. Erythroid response for subjects with a pretreatment hemoglobin of less than 9 g/dL will be defined as an increase in hemoglobin by  $\geq 1.5$ g/dL without packed red blood cell (PRBC) transfusion support, or a reduction in the units of PRBC transfusions by at least 50% during the eight consecutive weeks prior to response assessment - compared with the pretreatment transfusion number in the previous 8 weeks. Neutrophil response will be defined in those with a pretreatment absolute neutrophil count (ANC) of  $<0.5 \times 10^9/L$  as at least a 100% increase or an absolute increase  $> 0.5 \times 10^9/L$ . Subjects with a platelet, erythroid, and/or neutrophil response at 16 to 20 weeks may continue study medication (extended access) until they meet an off study criteria. Subjects with erythroid, or neutrophil response at 16 weeks may continue study medication for an additional 4 weeks (to ensure eligibility) prior to being consented for entry into the extended access part of the trial. Patients may remain on the extended access until they meet an off study criteria.

The toxicity profile will be measured using the CTCAE Version 4.0 criteria.

**Secondary endpoints** will include incidence of grade 2 or higher bleeding events as measured by

CTCAE v. 4.0; changes in serum thrombopoietin level, measured at 16 to 20 weeks; progression to higher risk MDS as measured by IWG criteria; and discontinuation of drug in robust responders enrolled in extended access.

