Subjects will initiate study medication at an oral dose of 50 mg/day (25 mg/day for East Asians), which will be adjusted as clinically indicated to the lowest dose that maintains a stable platelet count  $\geq 20,000/\mu\text{L}$  above baseline while maximizing tolerability. Treatment response will be any increase in a cytopenia, in the lineage that fulfilled eligibility criteria for enrollment and will be defined as: **(a)** platelet count increases to  $20,000/\mu\text{L}$  above baseline at 16 or 20 weeks, or stable platelet counts with transfusion independence for a minimum of 8 weeks in subjects who were previously transfusion dependent; **(b)** erythroid response for subjects with a pretreatment hemoglobin of less than 9 g/dL will be defined as an increase in hemoglobin by  $\geq 1.5\text{g/dL}$  without packed red blood cell (PRBC) transfusion support, or a reduction in the units of PRBC transfusions by at least 50% during the eight consecutive weeks prior to response assessment compared with the pretreatment transfusion number in the previous 8 weeks; **(c)** neutrophil response will be defined in those with a pretreatment absolute neutrophil count (ANC) of  $<0.5 \times 10^9/\text{L}$  as at least a 100% increase or an absolute increase  $> 0.5 \times 10^9/\text{L}$ . Subjects meeting a response may remain on the extended access until they meet an off study criteria or the study is closed.

Subjects with response at 16 or 20 weeks may be consented for entry into the extended access part of the trial. In the event that a subject is transfused platelets for a count  $>10,000/\mu\text{L}$  without a medical indication during the study period, the subject may continue on study drug and the response assessment may be extended for an additional 4 weeks, to week 20, at the discretion of the principal investigator. Subjects with evidence for a clinical response in any lineage at 16 weeks but not yet meeting full primary endpoint response criteria, and who are tolerating investigational treatment, may receive an additional 4 weeks of eltrombopag and be reassessed after 20 weeks. At that time, if they meet primary endpoint response criteria, they will be eligible to enter the extended access part of the study. If they do not meet primary endpoint response criteria, eltrombopag will be discontinued.

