### 5.2 Dose Adjustments (increases/decreases) of Eltrombopag (See section 2.6)

Patients will be enrolled on study because of anemia and/or thrombocytopenia. The majority of patients are expected to have cytopenias in both cell lines lineages, however some patients will have normal or close to normal counts in one or the other lineage at baseline. Therefore, dose adjustment criteria will vary depending on whether one or both lineages meet inclusion criteria, however dose adjustment will occur via the tables below and continue to the maximum dose until the inclusion criterion lineage or lineages responds, according to the schema set out below, unless toxicity-related stopping or dose reduction lab values occur. Note that patients entering the study based on anemia, with normal or near normal platelet count, will be expected to have an increased

in their platelet count on eltrombopag, but dose escalation for anemia will not be halted unless the platelet count goes above 400,000/ $\mu$ L. For patients entering meeting both anemia and thrombocytopenia eligibility criteria, dose escalation will not stop until both lineages reach the thresholds given below to stay on the current dose, unless platelets go over 400,000/ $\mu$ L or hemoglobin goes over 16.0 gr/dL, in which case drug will be discontinued for one week and the dose decreased by 50%. If the stopping platelet count or hemoglobin is reached regardless of entry criteria eltrombopag will be discontinued for one week and restarted at the next lowest dose.

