**Subjects who discontinue the study drug prematurely (before 20 weeks):** Platelet count measurement will be attempted even if a subject discontinues study drug. Important covariates for this study include age, karyotype, IPSS score, duration of platelet transfusion dependence, marrow cellularity and TPO level. The Cox proportional hazard model will be applied to time-to-event variables, such as time-to-death, time-to-relapse and time-to-progression. Since the sample size is relatively small, we will mostly consider Cox models with a single continuous or categorical covariate to ensure reasonable statistical accuracy. Such analysis is exploratory in nature and aimed at generating statistical hypothesis for future studies. Subjects who withdraw from the study for reasons other than lack of efficacy or toxicity (rendering platelet count missing) may be replaced. All other subjects should be evaluable for efficacy (i.e. all subjects who withdraw for treatment related concerns prior to end of week 16 or 20 assessment for toxicity or failure to respond will be counted as non-responders at the primary time points (intent to treat paradigm)). Based on the assumed dropout rate of 15-20% and the goal of having 25 evaluable subjects, 5 additional subjects may be enrolled.

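### Platelet response is defined in two ways, and read literally the 8.2 version lets a subject enrolled for anemia alone count as a responder with no change

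*Combined protocol and SAP*

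**What the plan says.** The primary response definition appears four times in the current text.

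- **8.1 Objectives**, in the paragraph giving the criteria for the primary endpoint, sets two limits. Response is "any increase in a cytopenia in the lineage that fulfilled eligibility criteria for enrollment", and the second platelet limb is "stable platelet counts with transfusion independence for a minimum of 8 weeks in subjects who were previously transfusion dependent".
- **Precis, treatment-response paragraph**, carries both limits; response is again "in the lineage that fulfilled eligibility criteria for enrollment and will be defined as" what follows.
- **8.2 Endpoints** opens with responders "as defined by changes in the platelet count and/or platelet transfusion requirements". It then defines platelet response as a rise of 20,000/µL at 16 to 20 weeks "or stable platelet counts with transfusion independence for a minimum of 8 weeks. Erythroid response". Neither limit appears.
- **Precis, primary-endpoint paragraph**, also omits both limits.

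In 8.2 and the Precis endpoint paragraph, the erythroid and neutrophil definitions keep their baseline conditions (hemoglobin below 9 g/dL; ANC below 0.5 × 10⁹/L). Only platelet response is open to every enrolled subject.

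Inclusion criterion 4.1.3 joins the platelet, hemoglobin and ANC criteria by OR ("OR hemoglobin less than 9.0 gr/dL or red cell"), so a subject can enter for anemia or neutropenia alone. Section 5.2 expects most subjects to have both anemia and thrombocytopenia, but adds that "some patients will have normal or close to normal counts in one or the other lineage at baseline".

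**The concern.** The unrestricted wording opens two routes to response that 8.1 closes.

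1. A subject enrolled for anemia or low ANC, never given platelets and with a stable count, satisfies the second limb without any change and without any drug effect.
2. A subject with a near-normal platelet count who gains 20,000/µL satisfies the first limb. This may well be a drug effect, and 5.2 expects platelets to rise in anemia entrants, but it is not improvement in the cytopenia that led to enrollment.

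The trial has one arm and one decision rule, and a single responder (5 versus 6 of 25) separates the two conclusions. If the choice of section is left to the analyst once the data are known, it amounts to choosing the primary endpoint after the fact. The interim look is exposed too: 8.3 aims to abandon an ineffective treatment early, and subjects who respond automatically make that less likely.

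**Working it through.** **Inputs.** From 8.3: null rate 10%, alternative 30%, significance level 0.05, power 0.8; 15 subjects in stage 1, stop with 1 or fewer responders; 25 in total, null accepted with 5 or fewer. Three quantities are not in the documents and are assumed: *f*, the expected share of subjects enrolled for another lineage with stable, never-transfused platelets; *k*, their actual number among 25; and *q*, the probability that such a subject meets the 8.2 limb.

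**Step 1: reproduce the design.** With X the stage 1 responders (n = 15) and Y the stage 2 responders (n = 10), both binomial with rate *p*,

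P(reject) = Σ over x = 2 to 15 of P(X = x) × P(Y ≥ max(0, 6 − x)).

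- p = 0.10: 0.0328
- p = 0.30: 0.8017
- P(stop at stage 1 | p = 0.10) = P(X ≤ 1) = 0.206 + 0.343 = 0.549

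A search over two-stage designs confirms that 1/15 and 5/25 is the minimax design. The stated design is correct; the problem lies in who is counted.

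**Step 2: affected subjects as a share.** Let the rest respond at 10%. The apparent rate is p = f·q + (1 − f)·0.10. For example, f = 0.10 and q = 1 give 0.10 + 0.09 = 0.19. Putting p into the step 1 formula gives the chance of declaring success:

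| f | q = 1 | q = 0.6 |
|---|---|---|
| 0 | 0.033 | 0.033 |
| 5% | 0.142 | 0.082 |
| 10% | 0.331 | 0.159 |
| 20% | 0.736 | 0.379 |

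**Step 3: affected subjects as a count.** Place exactly *k* affected subjects at random among the 25, so that the number falling in stage 1 is hypergeometric. Give them rate *q* and the rest 0.10, apply the same boundaries, and average over the placement:

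| k of 25 | q = 1 | q = 0.6 | q = 0.3 |
|---|---|---|---|
| 1 | 0.084 | 0.061 | 0.044 |
| 2 | 0.190 | 0.106 | 0.058 |
| 3 | 0.374 | 0.173 | 0.075 |

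Check of the k = 1, q = 1 entry: if the subject falls in stage 1 (probability 15/25) the result is 0.0847, and if in stage 2 (10/25) it is 0.0820. The average is 0.6 × 0.0847 + 0.4 × 0.0820 = 0.0836.

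**Step 4: effect on the interim look.** At a 10% rate the chance of passing stage 1 is 1 − 0.549 = 0.451. With k = 1 and q = 1 it is 0.643.

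These figures model only the stable-platelet limb. The 20,000/µL limb in subjects with near-normal platelets would add to them but is not quantified.

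**The case against.** The best reply is that 8.1 plainly governs. Its paragraph is introduced as the criteria for the primary endpoint, it stands immediately before 8.2, and the Precis treatment-response text agrees with it. Section 5.2 ties dose escalation to response in the lineage that met the inclusion criterion. The opening of 8.2 speaks of changes in platelet count or transfusion need, and a stable, never-transfused subject has changed in neither. On this view 8.2 is an incomplete restatement, and the harmful reading requires ignoring the rest of the document.

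As an account of intent this is probably right. It does not settle the rule. The section headed Endpoints and the Precis paragraph labeled as the primary endpoint both give the other wording, their operative sentence accepts stability with no prior-dependence condition, and no text sets an order of precedence.

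The objection to the size has more force. *f*, *k* and *q* have no anchor in the documents. What counts as stable is undefined, and subjects who withdraw for toxicity or failure to respond "will be counted as non-responders at the primary time points", so *q* may be well below 1. At q = 0.3, one affected subject leaves the error at 4.4%, under the nominal 5%; two bring it to 5.8%. The documents also do not name the product in transfusion independence. If red cells were included, the affected group would shrink to subjects not receiving them, but it would not be empty.

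Finally, 8.1 does not match 4.1.3 throughout. Red-cell-dependent entrants with hemoglobin of 9 g/dL or more fall outside the erythroid definition, and the ANC cut-off is at or below 500 at entry but strictly below 0.5 × 10⁹/L for response. Those mismatches are real, but they exist in all versions and are separate from this point.

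**Conclusion.** The concern holds. The primary endpoint carries two definitions of platelet response that classify some foreseeable subjects differently, and the documents do not say which prevails. The Simon design itself is sound (type I error 3.3%, power 80.2%).

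Under the literal 8.2 reading, with the remaining subjects responding at 10%, the nominal 5% is exceeded by a single affected subject among 25 if all such subjects meet the limb (8.4%) or if 60% do (6.1%), and by two if 30% do (5.8%). These are conditional illustrations, not estimates for this trial. The contradiction does not depend on them. Because it decides who is a responder in the only go/no-go test, it must be corrected.

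**What to change.** Before the primary analysis, replace the platelet wording in 8.2 and in the Precis primary-endpoint paragraph with the 8.1 definition, or a cross-reference to it, and state that this definition prevails wherever the wording differs. It should say that:

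1. response counts only in a lineage that met 4.1.3 at entry;
2. the transfusion-independence limb applies only to subjects who were platelet-transfusion dependent at entry, as 4.1.3 defines it (at least 4 platelet transfusions in the 8 weeks before entry). Section 8.1 gives no threshold of its own, and 4.1.3 is the only definition the documents contain.

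The cost is a wording change in two places. Sample size, stage boundaries and data collection stay as they are, since entry lineage and transfusion history are already needed to apply 4.1.3. The observed response rate may be lower than under the unrestricted wording.
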